### **Sham applicator**

Sham-ESWT will be performed to patients in Group B from the same machine. Sham-ESWT is the application of ESWT with a specially modified applicator that does not allow the penetration of shock waves into the tissue. A 3-4 cm thick pulp (air filled material) covered with medical latex material will be placed over the applicator. The modification is self-made, based on the knowledge of physical principles of ESWT.

The set intensity, frequency, total number of shocks and form of application will be the same as in group A, so the audio stimulus from the strength of the generated wave, the duration of application and sensitive sensations of skin movement will be similar in both groups. No side or therapeutic effects are expected with the applicator modified in this way.

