## **Study design and description**

This work is designed as a randomized, sham-controlled clinical trial in which we monitor the effects of low-energetic focused shock wave therapy (ESWT) on Achilles (AT) tendinopathy. We estimate that at least 18 patients will participate in it. They will be randomly divided into two groups in 1:1 ratio. Group A will receive ESWT according to selected parameters (see below). Group B will receive placebo in the means of sham-ESWT (see below).

Patients in both groups will have same program. The research within one patient will last in total of 8 weeks from the initial to the end examination. In the initial week the patient will be clinically examined by a physiotherapist, an ultrasonography (USG) examination will be performed and VISA-A questionnaire will be filled. At the end of this session, the patient will be randomly assigned to group A or B and receive first application (ESWT or sham-ESWT). For the next 4 weeks, once a week, the next applications will be performed. The interval between individual applications should be at least 5 days. Thus, a total of 5 applications of ESWT or sham-ESWT will be performed. The final examination will be performed at 3 weeks follow up after the last application and includes the same procedures as in the initial examination.

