## **Patient selection**

Patients will be included in the study if they meet these inclusion criteria:

- the patient complains about Achilles tendon pain, which limits (at least partially) his quality of life during daily activities or sport, and this condition could be referred as a tendinopathy
- the patient's other leg is asymptomatic
- the patient is not aware of the symptomatic mechanical tendon damage in past (eg. partial or complete rupture due to injury)
- the patient has no previous experience with ESWT

Patients will not be included if:

- the patient has condition which is contraindication for ESWT
- the patient has symptomatic mechanical tendon damage in past (eg. partial or complete rupture due to injury)
- the patient has previous experience with ESWT

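### The sham applicator has a latex cover, but no eligibility criterion addresses latex allergy, so a patient with known allergy could be assigned to five latex-covered applications

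*Combined protocol and SAP*

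**What the plan says.** The Sham applicator section describes the device used for every Group B treatment: "A 3-4 cm thick pulp (air filled material) covered with medical latex material will be placed over the applicator". On its basis the section says: "The modification is self-made, based on the knowledge of physical principles of ESWT". On safety it says: "No side or therapeutic effects are expected with the applicator modified in this way". Settings, shock count and manner of application are to match Group A, and the section states that "sensitive sensations of skin movement will be similar in both groups".

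Under Study design and description, the exposure count is fixed: "Thus, a total of 5 applications of ESWT or sham-ESWT will be performed".

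Patient selection has three exclusions. The only general medical one is that "the patient has condition which is contraindication for ESWT"; the contraindications are not listed. The second is earlier symptomatic mechanical damage to the tendon. The third is that "the patient has previous experience with ESWT". Neither the inclusion nor the exclusion list mentions latex or allergy.

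The Initial and final examination section starts with history taking but does not say what is asked, and does not link the history to eligibility. According to Patients distribution and randomization, assignment follows the initial examination.

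**The concern.** Latex is a hazard of the trial's own modification, not of shock waves. An exclusion worded around contraindications to ESWT does not, on its face, reach it, and the other two exclusions have nothing to do with it. A site that followed the eligibility list exactly could enrol someone with known latex allergy and, by chance, assign that person to the arm that uses the latex cover.

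The main stake is patient safety. The exposure occurs only in Group B, where the plan expects no therapeutic effect, so nothing offsets the risk, and it can be avoided. The secondary stake is interpretation: a skin reaction seen in one arm only, over the painful area, could be reported as pain.

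**Working it through.** **1. Does the cover reach the patient?** The latex is described as the covering of the air-filled pad, so it is the outer layer. The sham is meant to produce skin sensations like those of active treatment, which implies that the covered head is held against the leg. The ESWT application section uses ultrasound gel, and the sham follows the same form of application, so gel may lie between cover and skin. The plan does not present gel as a barrier. Contact is therefore a reasonable inference, not a stated fact.

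**2. Does the stated safety basis cover latex?** The rationale is the physics of ESWT. That supports the expectation that waves will not enter the tissue. It says nothing about skin tolerance of the cover.

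**3. Does any exclusion cover latex?**

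| Exclusion | Addresses latex allergy? |
|---|---|
| Contraindication to ESWT (not listed) | Not on its wording |
| Earlier symptomatic tendon damage | No |
| Earlier ESWT | No |

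**4. Exposure.** Inputs are from Study design and description (at least 18 patients, 1:1, one application in the initial week and one in each of the next 4) and ESWT application (500 shocks from each side, 300 dorsally, 10 Hz).

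- Applications per patient: 1 + 4 = 5, which reproduces the plan's figure.
- Shocks per application: 500 + 500 + 300 = 1300, which also agrees with the plan.
- Time per application: 1300 / 10 = 130 s.
- Time per sham patient: 5 × 130 = 650 s, about 10.8 minutes.
- Sham patients: 18 / 2 = 9. Sham sessions: 9 × 5 = 45.

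**5. Chance that a sensitive patient is in Group B.** The documents give no prevalence p, so the values below are assumptions. The formula is 1 − (1 − p)^9.

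| Assumed p | At least one among 9 |
|---|---|
| 0.5% | 4.4% |
| 1% | 8.6% |
| 2% | 16.6% |
| 5% | 37.0% |

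These are chances that a sensitive patient is present, not that a reaction occurs.

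**6. Which outcomes could a reaction touch?** VISA-A is completed at the initial and final examinations only, and the final one is 3 weeks after the last application. Maximal pain (NRS) is also recorded at the last application, the only outcome reading taken close to an exposure. One patient in 9 carries 1/9 (11%) of the group mean, so an assumed rise of d points in one patient moves the Group B mean by d/9. The Data analysis section frames its comparison as final against baseline, so even this reading is not clearly part of the main comparison.

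**The case against.** The strongest reply is that the gap may be closed in practice. Title and consent pages are not in the text available, and an allergy question could sit there. The contraindication list is not shown either. History is taken before assignment, and one investigator carries out the examinations and every application, so there is a natural moment to ask. This limits certainty about what happens at the site. It does not supply the missing criterion, because nothing in the eligibility list would exclude a patient who answered yes.

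A reader might also infer that the latex cover biases the trial in favour of ESWT by worsening VISA-A in Group B. The documents do not support this. A reaction would have to last three weeks after the last application and be reported as tendon trouble, on a questionnaire described as measuring perceived disease severity and its impact on activities.

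The same caution applies to blinding. Patients may not see the applicator, so a patient would have to connect a reaction with latex, and latex with sham. That is possible, but nothing in the plan makes it likely.

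Finally, the cover is part of a device designed to match sound and feel. Changing it is not free, and the plan does not show that another membrane would behave the same way. That stands and is reflected in the cost below.

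**Conclusion.** The point holds as a safety and eligibility gap. As written, the plan allows a patient with known latex allergy to be assigned to Group B and treated five times, about 130 s each time, with a latex-covered applicator. The stated expectation of no side effects rests on reasoning that does not concern the cover.

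The size is modest and uncertain. At 18 patients, about 9 would meet the cover, and the 4% to 37% range depends entirely on the assumed 0.5% to 5% prevalence. It would be wrong to apply the formula to all 18 patients and call the result an exposure risk, since Group A does not use the cover. It would also be wrong to read the plan as guaranteeing that the sham has no side effects: it says that none are expected. No sample-size or analysis figure changes. The conclusion assumes skin contact, possibly through gel, and that the pages not available contain no latex exclusion.

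**What to change.** Either of two changes is enough.

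- **Change the cover.** In the Sham applicator section, specify a latex-free membrane with similar acoustic and tactile behaviour. This removes the hazard for every patient, including those unaware of an allergy. The cost is rebuilding the device once and rechecking that it still blocks transmission and matches active treatment in sound and feel.
- **Keep latex and screen.** Ask every patient about known latex allergy at the initial examination, before assignment, and add it to the exclusions under Patient selection. Asking everyone applies the rule equally to both groups. The cost is one question and an occasional excluded applicant. It catches only allergies that patients know about.

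If a latex question already exists in pages not available here, it is enough to add the matching exclusion to Patient selection.

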**Graphically represented study design:**

## **Data analysis**

In this study, the comparison of the results in groups A and B in the final examination compared with the baseline values will be evaluated.

Firstly, descriptive statistics (mean, median, standard deviation, minimum and maximum) of the initial and final values in both groups will be performed. Normal data distribution will be determined by the calculated Shapiro-Wilk p-value.

Then, a two-way ANOVA tests will be used to evaluate the statistical significance of effects comparison in both groups for most of the measured parameters (not including the tendon loading tests). Also the Tukey method will be performed to determine effects of each part of ANOVA testing.

In addition, paired t-tests or the Wilcoxon test will be performed for each group of each parameter. Thus, the statistical significance of the changes in the most of the parameters for each group will be calculated.

The number of repetitions in Achilles tendon loading tests (single leg heel rise / hop test) will only be analyzed by descriptive statistics to see the indicative change in results. There will also be collected a number of those patients who describe the pain during these tests.

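### Shapiro-Wilk at about 9 patients per group is a weak, under-specified basis for choosing the within-group test, and the fixed between-group ANOVA has no prespecified robust check

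*Combined protocol and SAP*

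**What the plan says.** The Data analysis section of the combined protocol and SAP sets out four steps.

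- After descriptive statistics of the initial and final values: "Normal data distribution will be determined by the calculated Shapiro-Wilk p-value". No cut-off is given. The section does not say whether raw values, changes or residuals are tested, or whether this is done per group or pooled.
- Between groups: "Then, a two-way ANOVA tests will be used to evaluate the statistical significance of effects comparison in both groups for most of the measured parameters", leaving out the tendon loading tests. No alternative is named for use if normality is rejected.
- Post hoc: "Also the Tukey method will be performed to determine effects of each part of ANOVA testing".
- Within groups, introduced as an addition: "paired t-tests or the Wilcoxon test will be performed for each group of each parameter". The stated purpose is: "Thus, the statistical significance of the changes in the most of the parameters for each group will be calculated".

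The t-test/Wilcoxon pair is the only parametric/non-parametric choice in the plan. Its link to the Shapiro-Wilk sentence is implied, not written.

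On size, Study design and description says "We estimate that at least 18 patients will participate in it" and "They will be randomly divided into two groups in 1:1 ratio". That is about 9 per group at the minimum.

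**The concern.** A normality pre-test is least informative in small samples, where departures from normality matter most. With 9 patients per group, passing Shapiro-Wilk says little about the shape of the data, and whether a skewed sample is flagged is largely chance. Three consequences follow.

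- The same parameter may be tested by t in one arm and by Wilcoxon in the other, so the two within-group p-values cannot be read side by side.
- The samples that go on to the t-test are not made safe by having passed.
- With no cut-off and no tested variable stated, the choice can be settled after the data are seen.

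Separately, the analysis that does compare ESWT with sham has no prespecified residual check or robust sensitivity analysis. Its outcomes include bounded scores such as NRS and VISA-A.

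**Working it through.** **Inputs.** From the document: at least 18 patients, 1:1, so 18 / 2 = 9 per group. Assumed, because the document is silent: two-sided alpha 0.05, Shapiro-Wilk cut-off 0.05, and one pre-test per group on the changes. The document gives no operating characteristics for its rule, so there is no stated figure to reproduce. Results are simulated, with 10,000 runs per case in the table.

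**Formulas.** If each arm is tested once and independently, with rejection probability p, the chance that the arms get different tests is 2p(1 - p). With time as a repeated factor, the group-by-time interaction of the two-way ANOVA equals a two-sample t-test on change scores. It was computed that way, with the same shape in both arms.

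| Shape of changes | Shapiro-Wilk rejects, n = 9 | Arms get different tests, 2p(1 - p) | Paired t type I error, n = 9 | ANOVA interaction type I error, 9 vs 9 | Power at 1.4 SD: ANOVA / exact rank test |
|---|---|---|---|---|---|
| Normal | 5% | 9% | 5.0% | 5.2% | 80% / 74% |
| Uniform | 8% | 14% | 5.6% | 4.9% | 80% / 69% |
| t, 3 df | 17% | 28% | 3.9% | 4.2% | 85% / 89% |
| Gamma, skew 1 | 13% | 22% | 7.1% | 5.1% | 80% / 78% |
| Exponential | 39% | 48% | 10.1% | 4.1% | 81% / 85% |
| Lognormal, sigma 1 | 54% | 50% | 16.3% | 3.4% | 85% / 94% |

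**Step 1, detection.** For a milder lognormal (sigma 0.5), the rejection rate is about 22%. Of the shapes tried, only the lognormal with sigma 1 is flagged more than half the time.

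**Step 2, discordance.** For t with 3 df, 2 x 0.169 x 0.831 = 0.28. For lognormal sigma 0.5, 2 x 0.22 x 0.78 = 0.34. For exponential, 2 x 0.392 x 0.608 = 0.48. Direct simulation of both arms gave 28% for t with 3 df and 48% for exponential.

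**Step 3, does passing protect the t-test?** With exponential changes of mean zero, separate runs put the overall paired-t error at 10.1-10.8%, and at 12.6-13.1% among samples that passed Shapiro-Wilk. Skewed samples that happen to look normal are the ones in which the t-test errs more often.

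**Step 4, the between-group test.** In the table its error lies between 3.4% and 5.2%. Clipped and rounded scores, with assumed means and SDs and the same distribution in both arms (20,000 trials each), gave 4.8-5.2% for VISA-A at baseline means of 60, 75 and 85, and 5.0-5.3% for NRS at baseline means of 6, 4 and 3.

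**Step 5, unequal shapes.** With equal means, exponential changes in one arm and normal changes in the other, error at 9 vs 9 is 5.7%, 7.6% and 9.8% when the skewed arm's SD is 1, 2 and 3 times the other's. At 7 vs 11 with the smaller arm skewed, SD ratios of 2 and 3 give 10.7% and 14.7%. Opposite exponential skew in the two arms gives 8.5%. All of these are assumed scenarios.

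**Step 6, baseline adjustment.** For a 1.2 SD effect at 9 per arm, simulated power for the final value adjusted for baseline, against the change-score comparison, is 69% vs 53%, 76% vs 67% and 89% vs 87% at assumed initial-final correlations of 0.3, 0.5 and 0.7.

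**The case against.** The strongest reply is that the comparison of ESWT with sham does not pass through Shapiro-Wilk at all. The ANOVA is fixed in advance, and a fixed test is the opposite of one picked by a p-value. Its error holds under strong skew and with bounded scores, provided the arms share a shape. The t-test/Wilcoxon choice affects supplementary tests only. Nine per group is a floor: at 18 per group Shapiro-Wilk would flag 77% of exponential samples, though still only 31% for t with 3 df. With normal changes, choosing t or Wilcoxon by pre-test gave 5.2% error, the same as t alone. All of this stands, and it limits the point.

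A reader might infer more than the document supports.

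- **That the ESWT-sham comparison has no sound error control.** Steps 4 and 5 do not show this. Error rises only if shape or spread differs by arm. That could happen, for instance if only some ESWT patients respond, but nothing in the document establishes it.
- **That test choice is arbitrary throughout.** It is unstable only for the within-group tests.
- **That the wrong quantity is tested.** The sentence follows the descriptive statistics of initial and final values, which hints at raw values, but the document does not say. The supportable criticism is that the tested variable is unspecified.
- **That the number of pre-tests inflates the trial's error rate.** A false rejection with normal data merely swaps t for Wilcoxon. The chance of some false rejection among many pre-tests is not a trial error rate.

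What remains is an unreliable, incompletely written rule for the within-group tests, and no prespecified robust check on the comparison that matters.

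**Conclusion.** The point holds at minor to moderate severity. As a basis for choosing the within-group test, Shapiro-Wilk at about 9 per group misses roughly 61-83% of samples from clearly non-normal shapes (100 - 39 and 100 - 17). It leaves the arms on different tests in about 28-48% of cases. It does not prevent a paired-t error of about 10% under exponential changes, or about 13% among samples that pass. For the between-group ANOVA, the demonstrated cost is efficiency, for example 85% against 94% power for a rank test under lognormal changes with sigma 1. Inflation appears only under assumed differences in shape or spread.

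These figures rest on alpha and cut-off of 0.05, one pre-test per arm on the changes, 9 vs 9, and an ANOVA that treats time as a within-patient factor. The plan does not state that last point. If pairing were ignored, the interaction test would become conservative (2.1%, 0.8% and 0.1% error at correlations of 0.3, 0.5 and 0.7) and lose power.

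**What to change.** In the Data analysis section:

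1. Delete the Shapiro-Wilk rule. No p-value should choose a test.
2. For each continuous parameter now assigned to the two-way ANOVA, prespecify one between-group comparison: the final value adjusted for its baseline value (ANCOVA), reported as a group difference with its confidence interval.
3. Inspect residuals by plot.
4. Prespecify a rank or permutation test as a sensitivity analysis, reported whatever the plots show. A permutation must follow the actual allocation procedure. Patients distribution and randomization says that ultrasound findings influence group assignment but gives no mechanism, so that must be written down first.
5. Report within-group changes descriptively, or with one prespecified test used in both arms.

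The cost is SAP wording, a little code and one residual degree of freedom (18 - 3 = 15 instead of 18 - 2 = 16). No extra patients, visits or measurements are needed. The rank check is somewhat less powerful with normal data (74% against 80% at 1.4 SD), which is acceptable in a sensitivity analysis. On the simulations above, baseline adjustment gains power at each correlation tried.

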## **Patients distribution and randomization**

Patients will be randomly divided into two groups (Group A, Group B) in a 1:1 ratio. Patients in Group A will receive low-energetic focused ESWT according to selected parameters. Patients in Group B will receive placebo (sham-ESWT). The patients themselves will not know which group they are in. Before, during, and even after the session, patients will not be allowed to see the applicator or machine. The sham applicator will have to be always prepared before the patient come into the intervention room.

Due to the fact that AT tendinopathy includes a wider range of causes that can be monitored by USG examination, the finding on USG examination will also be taken into account when dividing into groups. In each group the specific cause should be represented in similar proportion. For this reason, the patient will be assigned to one of the groups only after the initial examination.

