## **Initial and final examination**

During the initial and final examinations, the several tasks to the patient will be performed. Firstly the anamnestic data will be collected, then the ankle dorsiflexion range of motion will be measured using the "weight-bearing lunge test" (cm). Thompson's test and resistance test will be

performed at the same time. The area of greatest pain will be localized by palpation. Then patient will also perform AT loading tests on both legs — single leg heel rise test and single leg hop test. The patient will perform as many heel rises/hops using only one leg as possible in 30 seconds or until first sign of pain in Achilles tendon area. This will be also measured in asymptomatic leg.

Secondly, the patient will be asked to complete a validated Victorian Institute of Sports Assessment - Achilles questionnaire, which assesses the subjectively perceived severity of the disease and partly its impact on the quality of normal daily or sports activities.

The patient's maximal pain will be assessed using a standardized numerical rating scale (NRS) of pain. The patient will be asked about the maximum pain that could be caused by various factors, at the initial examination, at the last application and during the final examination.

Lastly, the ultrasonographic examination of patient's AT in both legs will be performed. This examination is described in the following chapter.

Both, initial and final examinations in each patient will be performed by only one person (the investigator of the study) and the same person will prepare and perform each application of ESWT or sham-ESWT.

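### The only between-group test, a two-way ANOVA with Tukey, names no patient term and no decisive effect; ANCOVA on the initial value would be clearer and usually more precise

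*Combined protocol and SAP*

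**What the plan says.** The Data analysis section states its aim as follows: "the comparison of the results in groups A and B in the final examination compared with the baseline values will be evaluated". Descriptive statistics come first, "of the initial and final values in both groups will be performed". The only test that sets group A against group B is then given: "a two-way ANOVA tests will be used to evaluate the statistical significance of effects comparison in both groups for most of the measured parameters". A post-hoc step follows: "Also the Tukey method will be performed to determine effects of each part of ANOVA testing".

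The remaining tests are within group: "paired t-tests or the Wilcoxon test will be performed for each group of each parameter". The tendon loading tests are to be described only. Nothing else in the document supports a conclusion about ESWT against sham.

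Two other places bear on the model. Under Initial and final examination, maximal pain on the NRS is asked about "at the initial examination, at the last application and during the final examination", so it has three times, whereas the other measurements have two. Under Patients distribution and randomization, "the finding on USG examination will also be taken into account when dividing into groups".

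**The concern.** The factors can be inferred as group and time from the opening sentence and the descriptives. Three things cannot be inferred:

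- whether patient enters as a repeated-measures term;
- which row of the ANOVA table, or which Tukey contrast, decides whether ESWT beats sham;
- whether the last-application pain score is in the model.

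Pairing is explicit only in the within-group tests. The initial value, which is collected from every patient, is not used as a covariate.

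The gap matters because the rows of the table answer different questions. The group main effect averages the initial and final examinations, so it estimates half of the treatment effect. The interaction is the difference in change. No Tukey pair of cells equals the difference in change, because that contrast involves all four cells. If the choice is left until the results are visible, both the false-positive rate and the power depend on it.

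**Working it through.** **Inputs.** The minimum of 18 patients and the 1:1 ratio (Study design and description) give n = 9 per group. The document states no alpha, power, effect size, SD or initial-final correlation, and no calculation behind 18, so that figure cannot be reproduced. Assumed here: two-sided 5%, normal data, SD 1 at both times, no dropout, true effect 0 or 1 SD, and correlation ρ = 0.3, 0.5, 0.7, 0.8 or 0.9.

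**Step 1. ANOVA without a patient term (4n observations treated as independent).**

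- Interaction contrast: true variance 4(1−ρ)/n, variance used 4/n. The test is too conservative by a factor 1−ρ.
- Group main effect: true variance (1+ρ)/n, variance used 1/n. The test is too liberal by a factor 1+ρ. Its expected value under a 1 SD effect is (0 + 1)/2 = 0.5 SD.

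With many patients the group-effect false-positive rate tends to 2{1 − Φ(1.96/√(1+ρ))}. This gives 8.6, 11.0, 13.3, 14.4 and 15.5% at the five values of ρ. The limit does not fall towards 5%, so a larger sample does not repair it.

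**Step 2. Repeated-measures ANOVA on two times.** The interaction equals a t-test on the change scores, with variance 4(1−ρ)/n and 2n−2 = 16 df. At ρ = 0.5 the noncentrality is 1/√(4 × 0.5/9) = 2.12, and power is 51%.

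**Step 3. ANCOVA.** Its variance relative to the change score is

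(1+ρ)/2 × (2n−3)/(2n−4).

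At n = 9 and ρ = 0.5 this is 0.75 × 15/14 = 0.80. Break-even is ρ = 2 × 14/15 − 1 = 0.87.

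**Step 4. Simulation at 9 per group** (200,000 trials per scenario; Monte Carlo error of the false-positive rates about 0.1 point). Power is for a 1 SD effect.

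| ρ | 0.3 | 0.5 | 0.7 | 0.8 | 0.9 |
|---|---|---|---|---|---|
| No patient term: group effect, false positives % | 8.5 | 10.8 | 13.3 | 14.4 | 15.7 |
| No patient term: interaction, false positives % | 2.1 | 0.8 | 0.1 | <0.1 | <0.1 |
| No patient term: interaction, power % | 28 | 25 | 21 | 18 | 14 |
| Repeated measures: interaction, power % | 39 | 51 | 73 | 88 | 99 |
| ANCOVA, power % | 52 | 60 | 77 | 89 | 99 |
| Variance, ANCOVA / change score | 0.70 | 0.80 | 0.91 | 0.96 | 1.02 |
| Mean 95% CI width in SD, ANCOVA | 1.95 | 1.77 | 1.46 | 1.23 | 0.89 |
| Mean 95% CI width in SD, change score | 2.33 | 1.97 | 1.52 | 1.24 | 0.88 |

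The repeated-measures interaction and ANCOVA both hold 4.9% to 5.0% false positives. The Tukey comparison of final A with final B has 30% to 31% power.

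**Step 5. Larger samples, since 18 is a minimum.** At 20 per group the group-effect false-positive rate is still 8.4, 11.0, 13.3, 14.4 and 15.6%. ANCOVA v change-score power is 89 v 74%, 94 v 87% and 99 v 98% at ρ = 0.3, 0.5 and 0.7. Break-even rises to ρ = 0.95.

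**Step 6. Pain NRS at three times.** If the last-application value enters, the interaction has 2 df and Tukey covers 6 × 5/2 = 15 cell pairs instead of 4 × 3/2 = 6. Take a 1 SD effect at the last application only, with equal correlations between times. The interaction noncentrality is (n/2) × [(1/3)² + (2/3)² + (1/3)²]/(1−ρ) = 4.5 × (2/3)/(1−ρ) = 3/(1−ρ), on 2 and 32 df. The test then rejects in 41, 54, 78, 92 and 99.8% of trials, although the groups do not differ at the final examination. Restricted to initial and final, the interaction and ANCOVA each reject in 4.9% to 5.1%.

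**The case against.** The plan is silent rather than demonstrably wrong. Its aim is worded as a difference in change and its within-group tests are paired, so the term two-way ANOVA may well be shorthand for a mixed group-by-time model, whose interaction is a valid test. The inflated false-positive rate needs two unfavourable readings together: no patient term, and the group row taken as efficacy. With a patient term the group row has the correct size, and without one the interaction loses power but gives no excess of false positives. The advantage of ANCOVA rests on an unknown correlation. For pain, the section mentions only initial and final values, and the rejection rates in step 6 reflect a real effect at another time, not false positives.

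All of this is fair, and it limits the size of the concern. It does not remove it. Even on the charitable reading no effect is named as decisive, the Tukey step contains no contrast equal to the treatment effect, the third pain score has no stated role, and the initial value is left unused where it could add precision. High correlation cannot be excluded for tendon width and CSA; there ANCOVA gains little or nothing over a repeated-measures ANOVA.

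**Conclusion.** The concern holds, and the section should be corrected before the data are analysed. The omission is certain; its consequence depends on what was meant.

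- **If no patient term is meant:** reading the group row gives 1.7 to 3.1 times the nominal false-positive rate (8.5/5 to 15.7/5), and reading the interaction leaves 14% to 28% power for a 1 SD effect.
- **If repeated measures on two times is meant:** the test is valid. What remains is a modest loss against ANCOVA: 13 points of power at ρ = 0.3 (52 v 39%), 9 at 0.5 (60 v 51%), 4 at 0.7 (77 v 73%), 1 at 0.8 (89 v 88%) and none at 0.9.

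The figures assume normal data, equal SDs, 9 per group and the stated range of correlations. They describe the methods and do not predict this trial's results.

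**What to change.** Replace the two-way ANOVA and Tukey sentences with wording such as:

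> For each continuous parameter, the final value is compared between A and B by ANCOVA with group as factor and the initial value as covariate. The adjusted difference A minus B is reported with its 95% CI and p-value. This comparison, not the within-group tests, is the basis for between-group conclusions.

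For pain NRS, state that the final examination is the endpoint and that the last-application value is analysed in the same way as secondary. State before analysis whether the USG category used in allocation enters the model, and with which levels. Name the parameters covered, including whether VISA-A and NRS are among them, and the leg analysed; the loading tests stay descriptive.

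If ANOVA is kept, the minimum repair is to name group and time (initial and final only, including for NRS) as factors, patient as the repeated-measures term and the group-by-time interaction as the decisive test, and to drop the Tukey step.

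**Cost.** Wording only, since the initial values are already collected. ANCOVA uses one degree of freedom for the initial value and one for each USG level beyond the first. At 9 per group and ρ = 0.5, power is 60% without a USG factor and 60, 59 and 58% with 2, 3 and 4 levels, if the levels are evenly spread and predict nothing. ANCOVA also assumes a common linear slope on the initial value, which should be checked by plot.

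This does not settle the primary outcome, multiplicity across parameters, the consequence of a failed Shapiro-Wilk test for the between-group comparison, or the analysis of visually graded USG findings.
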